8.2.2 Pharmacokinetic Analyses

PK data will be listed in the population PK-report for all patients with available PM01183 concentrations. PK analysis of plasma concentration-time data of PM01183 will be performed using non-linear mixed-effects modeling and/or non-compartmental analysis. Data may be combined with those of a selection of phase I or II studies to support a relevant structural model. Available patient characteristics (e.g., demographics, laboratory variables, genotypes) will be tested as potential covariates affecting PK parameters.

8.2.3 Pharmacogenetic Analyses

The influence of known polymorphisms on main PK parameters will be assessed by Student's test or Mann-Whitney's U test as appropriate.

8.2.4 Pharmacogenomic Analyses

Analysis of RNA/protein expression, polymorphisms and mutations will be performed blind and with clinical data compiled only after all analyses are completed. A Fisher's exact test/logistic regression for categorical variables and log rank test/Cox regression for time to event variables will be used to test whether a specific profile is associated with clinical outcome. The prognostic value of markers will be explored for objective response, PFS and OS. In each case, if applicable, a multivariate model will be developed by stepwise selection. All tests of statistical significance will be two-sided, and significance will be set at 0.05.

8.2.5 Safety Analyses

AEs, SAEs, deaths, laboratory evaluations, dose delays/reductions and study drug discontinuations due to AEs will be tabulated in a descriptive way. Counts and percentages will be used for categorical variables, and summary tables will be used for continuous variables.

8.3 INTERIM ANALYSES

An interim analysis to reject H₀ (non-binding) or to reject H₁ (futility) in each tumor type is planned after the recruitment of 15 evaluable patients in each cohort. The Gamma family boundary will be used to control the type I error, the parameter to reject H₀ is fixed as -1 and the parameter to reject H₁ is fixed as 0. If none of the first 15 evaluable patients in a determined cohort has a confirmed response, the alternative hypothesis will be rejected, according to boundaries and sample size assumptions, and recruitment will be stopped. If the number of responding patients is already two or more at the interim analysis, then H₀ could be rejected and the study will have enough power to be stopped. On the contrary, if there is one confirmed response, the recruitment will be continued to up to 25 evaluable patients.

In particular, in the SCLC and endometrial carcinoma cohorts, the analysis at 25 evaluable patients will serve as second interim analysis to decide the continuation of recruitment. Two objective responses will be required to expand the accrual up to 100 and 50 evaluable patients respectively.

- For the SCLC cohort, the type I/II error will be controlled with a Gamma family boundary (-1 to reject Ho, 0 to reject H1)
- For the endometrial carcinoma cohort, the type I/II error will be controlled with a Gamma family boundary (-1 to reject Ho, -3 to reject H1)

9. ADMINISTRATIVE SECTION

9.1 ETHICS

This clinical trial will be conducted in accordance with the ethical principles that have their origin in the World Medical Association (WMA) Declaration of Helsinki (see [APPENDIX 5](#)) and will be consistent with GCP guidelines and pertinent regulatory requirements.

The study personnel involved in conducting this trial will be qualified by education, training and experience to perform their respective task(s).

The study will be conducted in compliance with the protocol. The protocol, any amendments and the patient informed consent will receive Competent Authorities and IEC/IRB approval/favorable opinion prior to initiation, according to pertinent regulations.

The decision of the Competent Authorities and the IEC/IRB concerning the conduct of the study will be made in writing to the Investigator, and a copy of this decision will be provided to the Sponsor before the beginning of the study.

The Investigator and/or the Sponsor is/are responsible for keeping the Competent Authorities and the IEC/IRB informed of any significant new information about the study drug.

All protocol amendments will be agreed upon by the Sponsor and the Investigator.

Administrative changes of the protocol are minor corrections and/or clarifications that have no impact on the way the study is to be conducted.

9.2 MONITORING, AUDITING AND INSPECTING

The study will be monitored by regular site visits and telephone calls to the Investigator by the clinical trial monitor designated by Pharma Mar S.A.

During site visits, the trial monitor should revise original patient records, drug accountability records and document retention (study file). Additionally, the trial monitor should observe study procedures and will discuss any problems with the Investigator.

Adequate time for these visits should be allocated by the Investigator. The Investigator should also ensure that the monitor is given direct access [as per International Conference on Harmonization (ICH) Topic E6 Guideline for Good Clinical Practice, Sections 4.9.7 and 6.10] to source documents (i.e., hospital or private charts, original laboratory records, appointment books, etc.) of the patient which support data entered in the case report forms, as defined in the ICH Topic E6 Guideline for Good Clinical Practice, Sections 1.51 and 1.52.

Systems and procedures will be implemented to ensure the quality of every aspect of the trial.

During the course of the trial, the Clinical Quality Assurance Department of Pharma Mar S.A. or external auditors contracted by the Sponsor may conduct an onsite audit visit (ICH Topic E6 Guideline for GCP, Section 1.6).

Participation in this trial implies acceptance of potential inspection by national or foreign Competent Authorities.

9.3 PATIENT INFORMED CONSENT

The rights, safety and well-being of the trial patients are the most important considerations and should prevail over interests of science and society.

The ICFs will include all elements required by ICH, GCP and applicable regulatory requirements.

Prior to inclusion into the trial, the Investigator or a person designated by the Investigator, must provide the patient with one copy of the Informed Consent Forms (ICFs). This copy must provide written full information about the clinical trial, in a language that is non-technical and easily understood, as well as on other sub-studies (PGx/pharmacogenetic analyses). The Investigator should allow the necessary time for the patient or his/her legally acceptable representative to inquire about the details of the clinical trial; then, the ICFs must be freely signed and personally dated by the patient and by the person who conducted the Informed Consent discussion before the beginning of the study. The patient should receive a copy of the signed ICFs and any other written information provided to study patients prior to participation in the trial.

During a patient's participation in the trial, any updates to the consent forms and any updates to the written information will be provided to him/her.

If there is a need to obtain new consent from the patients, the Investigator or a person designated by the Investigator should inform the patients of any new information relevant to the patients' willingness to continue participation in the study, before obtaining the written consent.

9.4 CONFIDENTIALITY/PATIENTS IDENTIFICATION

The collection and processing of personal data from the patients enrolled in this clinical trial will be limited to those data that are necessary to investigate the efficacy, safety, quality and usefulness of the study drug used in this trial.

It is the Investigator's responsibility that sufficient information on the identity of the patients will be retained.

The trial monitor, the Sponsor's auditor, the IECs/IRBs and the Competent Authorities should have direct access to all requested trial-related records, and agree to keep the identity of study patients confidential.

The data must be collected and processed with adequate precautions to ensure confidentiality and compliance with applicable data privacy protection laws and regulations. Patients' personal data will be collected, processed and transmitted in a pseudonymised form.

Explicit consent for the processing of personal data will be obtained from the participating patient before data collection, if applicable, and this consent should also address the transfer of the data to other entities and countries.

The Sponsor shall comply with General Data Protection Regulation (GDPR) (EU) 2016/679 effective from 25 May 2018 (repealing Directive 95/46/EC GDPR of 24 October 1995), and applicable regulations on the protection of individuals with regard to the processing of personal data and on the free movement of such data.

9.5 CASE REPORT FORMS

CRFs will be used to record all data for each patient. It is the responsibility of the Investigator to ensure that the CRFs are properly and completely filled in, in English. CRFs must be completed for all patients who have given their informed consent.

A patient's source documentation is the patient's records (including but not limited to physician/hospital notes, nurses notes, IMP preparation records including reconstitution and dilution, IMP administration records, etc.) and any original document, and as such they should be maintained at the study site.

The data collected in the CRF will be entered into the Sponsor' databases, which comply with General Data Protection Regulation (GDPR) (EU) 2016/679 effective from 25 May 2018 (repealing Directive 95/46/EC GDPR of 24 October 1995) on the protection of individuals with regard to the processing of personal data.

9.6 INSURANCE

The Sponsor will provide insurance or indemnity in accordance with the applicable regulatory requirements.

9.7 RETENTION OF RECORDS

The Investigator/Institution should maintain trial documents according to Section 8 of the ICH Topic E6 Guideline for Good Clinical Practice and as required by applicable regulatory requirements.

Essential documents should be retained as per the aforementioned ICH guideline or for a longer period of time, if required by the applicable regulations.

9.8 USE OF INFORMATION AND PUBLICATION

Before the investigators of this study submit a paper or abstract for publication or otherwise publicly disclose information concerning the study drug or products, Pharma Mar S.A. must be provided with at least 60 days to revise and approve the proposed publication or disclosure to ensure that confidential and proprietary data are protected.

If Pharma Mar S.A. determines that patentable patient matter is disclosed in the proposed publication or disclosure, the publication or disclosure will be withheld for a period of time considered convenient. If the study is part of a multicenter study, the first publication of the study shall be made in conjunction with the presentation of a joint, multicenter publication of the study results with the investigators and the institutions from all appropriate sites that are contributing data, analysis and comments. However, if such a multicenter publication is not submitted within 12 months after conclusion, abandonment or termination of the study at all sites, the present study may be published individually in accordance with the procedure established above.

The order of the coauthors will reflect the relative contribution of each one to study development and analysis. In general, the first author will be the investigator who recruits the highest number of patients with information finally available for data analysis. Relevant Pharma Mar S.A. personnel who have fully participated in the study must be considered for co-authorship of the publication.

11. APPENDICES

APPENDIX 1: ECOG PERFORMANCE STATUS ASSESSMENT SCALE

Grade	ECOG PS*
0	Fully active, able to carry on all pre-disease performance without restriction
1	Restricted in physically strenuous activity but ambulatory and able to carry out work of a light or sedentary nature, e.g., light house work, office work
2	Ambulatory and capable of all self-care but unable to carry out any work activities. Up and about more than 50% of waking hours
3	Capable of only limited self-care, confined to bed or chair more than 50% of waking hours
4	Completely disabled. Cannot carry on any self-care. Totally confined to bed or chair
5	Dead

*As published in *Am. J. Clin. Oncol* 5:649-655, 1982: Oken, M.M., Creech, R.H., Tormey, D.C., Horton, J., Davis, T.E., McFadden, E.T., Carbone, P.P.: *Toxicity And Response Criteria Of The Eastern Cooperative Oncology Group.*

APPENDIX 2: CONTRACEPTION AND PREGNANCY TESTING.

This document is based on the Heads of Medicines Agencies' Recommendations Related to Contraception and Pregnancy Testing in Clinical Trials, published by the Clinical Trial Facilitation Group (CTFG) on 15 September 2014 and available at <http://www.hma.eu/ctfg.html> (accessed 30 July 2015).

A woman is considered of childbearing potential (WOCBP) following menarche and until becoming post-menopausal unless permanently sterile. Permanent sterilization methods include hysterectomy, bilateral salpingectomy and bilateral oophorectomy. A postmenopausal state is defined as no menses for 12 months without an alternative medical cause. A high follicle stimulating hormone (FSH) level in the postmenopausal range may be used to confirm a post-menopausal state in women not using hormonal contraception or hormonal replacement therapy. However, in the absence of 12 months of amenorrhea, a single FSH measurement is insufficient. Immediately after detecting a case of pregnancy in a patient, the decision on her continued participation in the clinical trial will be jointly taken by the patient, the Investigator and the Sponsor, with the patient's best interest in mind. A decision to continue the pregnancy will require immediate discontinuation any investigational medicinal product (IMP).

A man is considered fertile after puberty unless permanently sterile by bilateral orchidectomy. Fertile male patients included in this study should refrain from fathering a child or donating sperm during the study and for four months following the last IMP dose. If they have WOCBP partners the male subject should use condom during treatment and for four months following the last IMP dose.

Highly effective birth control methods are:

1. Combined (estrogen and progestogen containing) hormonal contraception associated with inhibition of ovulation ¹:
 - a. oral
 - b. intravaginal
 - c. transdermal
2. Progestogen-only hormonal contraception associated with inhibition of ovulation ¹:
 - a. oral
 - b. injectable
 - c. implantable ²
3. Intrauterine device (IUD) ²
4. Intrauterine hormone-releasing system (IUS) ²
5. Bilateral tubal occlusion ²
6. Vasectomized partner ^{2,3}
7. Sexual abstinence ⁴
8. Combinations of male condom with either cap, diaphragm or sponge with spermicide (double barrier methods) are also considered acceptable, but not highly effective, birth control methods.

¹ Hormonal contraception may be susceptible to interaction with the IMP, which may reduce the efficacy of the contraception method (see below).

² Contraception methods that are considered to have low user dependency.

³ Vasectomized partner is a highly effective birth control method provided that partner is the sole sexual partner of the WOCBP trial participant and that the vasectomized partner has received medical assessment of the surgical success.

⁴ Sexual abstinence is considered a highly effective method only if defined as refraining from heterosexual intercourse during the entire period of risk associated with the study treatments. The reliability of sexual abstinence needs to be evaluated in relation to the duration of the clinical trial and the preferred and usual lifestyle of the subject. Periodic abstinence (calendar, symptothermal, post-ovulation methods), withdrawal (coitus interruptus), spermicides only, and lactational amenorrhea method (LAM) are not acceptable methods of contraception. Female condom and male condom should not be used together.

Contraception methods with low user dependency should preferably be used, in particular when contraception is introduced as a result of participation in this trial. It cannot be excluded that the IMP may reduce exposure to substrates of CYP3A through enzyme induction; the efficacy of hormonal contraceptives may be reduced if co-administered with this drug.

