4.2 EXCLUSION CRITERIA

- 1) Prior treatment with PM01183 or trabectedin.
- 2) Prior or concurrent malignant disease unless in complete remission for more than five years, except treated *in situ* carcinoma of the cervix, basal or squamous cell skin carcinoma, and *in situ* transitional cell bladder carcinoma.
- 3) Known central nervous system (CNS) involvement. In patients with SCLC, brain computed tomography (CT)-scan or MRI results must be provided at baseline.
- 4) Relevant diseases or clinical situations which may increase the patient's risk:

- a) History within the last year or presence of unstable angina, myocardial infarction, congestive heart failure, or clinically relevant valvular heart disease or symptomatic arrhythmia or any asymptomatic ventricular arrhythmia requiring ongoing treatment.
 - b) Grade ≥ 3 dyspnea or daily intermittent oxygen requirement within two weeks prior to the study treatment onset.
 - c) Active infection.
 - d) Unhealed wounds or presence of any external drainage.
 - e) Known chronic active hepatitis or cirrhosis.
 - f) Immunocompromised patients, including known infection by human immunodeficiency virus (HIV).
- 5) Women who are pregnant or breast feeding and fertile patients (men and women) who are not using an effective method of contraception. *
 - 6) Impending need for RT (e.g., painful bone metastasis and/or risk of spinal cord compression).
 - 7) Limitation of the patient's ability to comply with the treatment or to follow-up the protocol.

* Women of childbearing potential (WOCBP) must agree to use an effective contraception method to avoid pregnancy during the course of the trial (and for at least three months after the last infusion). Valid methods to determine the childbearing potential, adequate contraception and requirements for WOCBP partners are described in [APPENDIX 2](#). Fertile men must agree to refrain from fathering a child or donating sperm during the trial and for four months after the last infusion.

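### Appendix 2 warns that the study drug may weaken hormonal contraception but requires no back-up, so a hormonal method alone satisfies the entry criteria

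*Protocol*

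**What the plan says.** Inclusion criterion 10 (Protocol section 4.1) asks fertile women for one medically acceptable method, during treatment and for at least three months afterwards. Exclusion criterion 5 (section 4.2) removes fertile patients who lack an effective method. Its footnote sends the site to Appendix 2 for the detail: "Valid methods to determine the childbearing potential, adequate contraception and requirements for WOCBP partners are described in" that appendix.

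Appendix 2 opens its list with "Highly effective birth control methods are". Items 1 (combined) and 2 (progestogen-only) are hormonal and carry footnote 1: "Hormonal contraception may be susceptible to interaction with the IMP, which may reduce the efficacy of the contraception method". The footnote points to the text below it. There the closing paragraph says "It cannot be excluded that the IMP may reduce exposure to substrates of CYP3A through enzyme induction" and adds that "the efficacy of hormonal contraceptives may be reduced if co-administered with this drug". The appendix ends at that point.

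The nearest thing to guidance is in the same paragraph: "Contraception methods with low user dependency should preferably be used". Item 8, double-barrier methods, sets a lower tier; these "are also considered acceptable, but not highly effective, birth control methods".

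**The concern.** The appendix doubts a method and leaves it on the approved list without saying what the site should do. Elsewhere in the same appendix, a condition is spelled out. A vasectomized partner counts only if he is the sole partner and the surgery has been checked. Abstinence counts only if it is complete over the whole risk period. Male patients with partners of childbearing potential are told to use a condom. Footnote 1 has no counterpart to these.

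What is at stake is participant safety. Protocol section 1.10.1.2 describes a drug that leads to DNA double-strand breaks, and section 7.7.3 makes pregnancy immediately reportable. A site that follows the text to the letter may treat a woman whose only contraception is one that the protocol itself says may be weakened. The objectives, the response endpoint and the sample size are not affected.

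**Working it through.** The plan gives no figure to reproduce. The check sets the relevant texts side by side and counts entries in Appendix 2.

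**Step 1: does a footnote-1 method alone satisfy the criteria?** Inclusion 10 needs one acceptable method and exclusion 5 needs an effective one. The exclusion footnote points to Appendix 2, which classes items 1 and 2 as highly effective. So yes, a single such method is enough.

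**Step 2: is any action attached to the caution?**

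- Highly effective methods: items 1 to 7, so 7. Item 8 describes itself as not highly effective.
- With footnote 1: items 1 and 2, so 2 of 7. Named forms: 3 (oral, intravaginal, transdermal) + 3 (oral, injectable, implantable) = 6.
- Forms with a required back-up, switch or restriction: 0 of 6.

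**Step 3: does other text supply the action?**

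- *Low-user-dependency preference (Appendix 2).* It is advisory and concerns user error, not the interaction. The methods marked as low dependency are the implant and items 3, 4, 5 and 6, so 5. Four carry no footnote 1; the fifth, the implant, does. A woman who follows the preference can still end up on a flagged method.
- *Section 6.7.3.* It examines inhibition of CYP3A4 by the study drug and advises caution with its substrates. It mentions neither induction by the study drug nor contraceptives. Its advice to monitor or avoid inducers and inhibitors concerns the effect of other drugs on lurbinectedin.
- *Pregnancy tests (section 5.7).* Testing on Day 1 of each cycle, before the infusion, detects a conception. It does not prevent one.
- *Condom instruction (Appendix 2).* It is written for male patients.

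**Step 4: are alternatives already listed?** Items 3 to 7 carry no footnote 1: 7 − 2 = 5 methods. Four of these (3, 5, 6 and 7) are non-hormonal.

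**Step 5: how many women?** This cannot be computed, because the documents give neither the number of hormonal-method users nor failure rates. Some cohorts will hold few. More than 90% of women with endometrial cancer are over 50 (section 1.5), most biliary cases occur after 60 (section 1.4), and over 90% of germ cell tumors arise in the testes (section 1.8). Others can hold some: the Ewing series in section 1.9 has a median age of 15 and 41% females, with enrolment here from 18, and the BRCA breast cohort is also open to younger women.

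**The case against.** The strongest reply is that no requirement is broken. The floor is modest, and item 8 accepts methods below the highly effective tier, so a somewhat weakened hormonal method might still clear it. On this view the appendix warns, exclusion 5 asks whether the method is effective, and the investigator judges. A reader might infer that the protocol admits women whose contraception fails its own standard. The documents do not support that, because nothing shows how far efficacy would fall. What stands is narrower: the site gets a warning and no rule for acting on it.

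Second, the hazard itself is thinly supported. Section 6.7.3 raises only inhibition, which would not lower hormone exposure, and its mechanistic static model gives an AUC ratio of 1.01. Reading Appendix 2 as evidence that lurbinectedin induces CYP3A would go too far: the wording is precautionary and no induction data are shown. This objection stands and limits severity. It does not explain why the protocol states the caution and then leaves it without consequence.

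Third, the hormone-releasing intrauterine system. A reader might infer that it falls under the caution, since the closing sentence speaks of hormonal contraceptives generally. The more natural reading is that it does not. Footnote 1 is assigned selectively: the implant falls under it, the intrauterine system carries only footnote 2, and footnote 1 is what points to the closing paragraph.

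Fourth, one might try to size the risk from the half-life of about 60 hours and the 21-day cycle. That would describe drug presence after any contraceptive failure, hormonal or not, and needs an assumed washout. It does not measure this gap.

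Finally, consent pages are not in the review copy, so instructions given there to participants cannot be checked.

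**Conclusion.** The point holds as a cheap improvement of low severity. Appendix 2 accepts items 1 and 2 as highly effective, says that the study drug may reduce their efficacy, and requires no action for any of their six forms. The soft measures narrow the gap without closing it. The conclusion rests on the wording and cross-references of the visible protocol. It does not depend on induction being real, and it does not claim that a hormonal method falls below the protocol's floor. The number of women exposed is unknown and probably small in several cohorts. Nothing in the efficacy analysis changes.

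**What to change.** Add one rule to Appendix 2: as long as CYP3A induction by the study drug has not been ruled out, a woman using a method that carries footnote 1, implants included, must add a barrier method or use a listed highly effective method without footnote 1, during treatment and for three months after the last infusion. If the sponsor holds data that exclude induction, deleting the caution would settle the matter equally well.

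Optional: a short clarification that the hormone-releasing intrauterine system is not covered by footnote 1.

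The rule adds no visit, test or data item. Its downside is a slightly stricter requirement for women on hormonal methods. It is also more than an editorial change: under section 9.1 an amendment needs approval from the Competent Authorities and ethics committees, and the consent form would probably need updating (section 9.3). It could sensibly travel with the next amendment made for other reasons.
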